11.4.1 Datasets to be analysed, analysis populations

ICH: The selection of subjects to be included in the analyses (e.g., all randomized subjects, all dosed subjects, all eligible subjects, evaluable subjects).

The data of all participants and measurement methods will be analysed. Subgroups typically composed are hearing loss dependent groups (mild, moderate, severe, profound) and groups depending on their experience level wearing hearing instruments or using accessories (non-experienced, short-term, experienced, long-term user). In case of a subject withdrawal, the statistician will decide if the data can be used for a part of the statistical analysis or if the data will be dropped out completely.

11.4.2 Primary Analysis

The primary analysis will be done by the statistician with help of appropriate software programs (e.g. Matlab, Statistica) by the end of the study (end of the pre-study and end of the main study).

11.4.3 Secondary Analyses

The secondary analysis is done in the same way as the primary analysis.

11.4.4 Interim analyses

ICH 6.9.1: including timing of any planned interim analysis(ses).

The procedure for each study is, to first make a pre-study with a small group of participants. After the pre-study an analysis is done, which can be also named interim analysis. Several pre-studies may be carried out. If the results of the pre-study (the pre-studies) do not look promising, it is decided whether to review the study design or to discontinue the study completely. If the results of the pre-study are sufficient one will continue with the main study.

11.4.5 Safety analysis

The safety analysis will be done permanently during the study by the PI.

11.4.6 Deviations from the original statistical plan

(ICH/E6 6.9.6)

ICH: Procedures for reporting any deviation(s) from the original statistical plan (any deviation(s) from the original statistical plan should be described and justified in protocol and/or in the final report, as appropriate).

Deviation(s) from the original statistical plan will be described and justified in a protocol and in a final report, as appropriate.

11.5 Handling of missing data and drop-outs

(ICH/E6 6.9.5; AGEK 8.5; SPIRIT 20c)

ICH: Procedure for accounting for missing, unused, and spurious data.

If data records are complete from subjects who dropped out of the study early, these data will also be used in the analysis. If the data sets are not complete, they will not be integrated in the analysis.

12. QUALITY ASSURANCE AND CONTROL

(ICH/E6 6.11, 6.13; AGEK 12; SPIRIT #19, 23, 27)

ICH: Quality Control and Quality Assurance Procedures

This section describes how quality is assured and controlled.

12.1 Data handling and record keeping / archiving

(Clin O, Art. 18, 45, 57, 62; ICH/E6 6.13; AGEK 12; SPIRIT #19, 27)

ICH: Data Handling and Record Keeping

All data and documents recorded during the study are only accessible to the clinical study team and to the monitor. Results from the laboratory measurements are stored automatically by the corresponding measurement tool in an appropriate format (e.g. xls file). The personal data, the source data of measurements, the documents inclusive all notes get coded and monitored. The code list for the codification is safely kept within the clinical study team.

All listed clinical investigators have access to the code list. This code list is not accessible to other people. The whole original data and personal data are accessible to the whole clinical study team. The study data are to undergo a comprehensive analysis. A written final report containing all phases of the study as well as a summary is to be written after the study is finished and is available to Sonova headquarters. The participants names have to be coded when they have to be used in an analysis.

At the end of the study all of the collected data, either collected in paper form or electronically, will be saved in an investigator site file (ISF) on CD or DVD. The ISF will be archived at Sonova AG Stäfa. The final data export will be stored electronically and in paper form.

12.1.1 Case Report Forms

(ICH/E6 6.4.9)

ICH: The identification of any data to be recorded directly on the CRFs (i.e., no prior written or electronic record of data), and to be considered to be source data.

Study data is recorded both with paper and with electronic Case Report Forms (p/eCRF). For each enrolled study participant a CRF is maintained. All CRFs are kept current to reflect the subject's status at each phase during the course of study. Participants cannot be identified in the CRF by name or initials and birth date but an appropriate coded identification is used, e.g. VP10SL15 containing the subject number and the study identifier. All study team members are authorized for the CRF entries and it is assured that any authorised person can be identified both for pCRFs and eCRFs. If pCRFs are used, the investigator's acronym as well as the subject ID is filled in and data are entered into an electronic file for analysis by the respective investigator and data get monitored by the assigned monitor. In case of a self-evident corrections, either the subject does it by himself or the investigator undertakes the correction by crossing out the word/sentence with a single horizontal line and by adding the correction including his personal identifier and the date.

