6.1 General study design and justification of design

(ICH/E6 6.4.2, 6.4.5; AGEK 4.2; SPIRIT #8)

ICH: The scientific integrity of the trial and the credibility of the data from the trial depend substantially on the trial design.

ICH: A description of the type/design of trial to be conducted (e.g., double-blind, placebo-control led, parallel design) and a schematic diagram of trial design, procedures and stages.

ICH: The expected duration of subject participation, and a description of the sequence and duration of all trial periods, including follow-up, if any.

A methodical evaluation of novel sound changing principles in CE-Labelled Sonova brand hearing instruments (primarily Phonak hearing instruments) is intended to be conducted on hearing impaired and normal hearing subjects. This will be a controlled, single blinded (participants), randomised (sequence of test procedure and sequence of tested setting/device), cross-over (investigational product/setting) active comparator study which will be conducted mono centric at Sonova AG Headquarters based in Stäfa.

Treatments/Interventions:

Hearing systems (hearing instruments with hearing instrument software and respective acoustic coupling, fitting software and wireless accessories). All CE labelled MDs.

Population:

Adult participants with different degrees of hearing abilities. In the pre-studies it is planned to include up to 5 participants. The main studies will normally include 20 - 25 participants each. If possible a power analysis is carried out for each study to determine the necessary number of subjects.

Level and method of blinding/masking:

The tests will be at least single blinded.

When testing different parameter settings of the novel application and/or comparing novel with previous applications whereas these approaches are available as optional settings in one hearing instrument, the subjects will not know which setting is activated during the respective testing.

In cases where these settings are not accessible in one hearing instrument (e.g. previous sound changing principle is not supported by the latest hearing instrument technology any more), the test needs to be undertaken with several (two) separate hearing instruments, whereas the housing of these hearing instruments may differ. The subjects will not be informed about the setting or the sound changing principle in the specific hearing instrument.

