6.2.1 Randomization

As this is a controlled cross-over study each subject serves as his or her own control. For the reduction of order effects the sequence of the tested settings (and/or tested devices) will be randomized. To do so block randomization will be used. The randomization is applied to all investigational settings for both the laboratory trials and the trials in real world environment. For sub-studies with several test methods the order of the test methods will be also randomized with help of block randomization. Randomization and concealment of randomization list is generated by the Principle Investigator. For laboratory tests where several individual ratings are executed with help of computer controlled testing procedures (e.g. software tool for MUSHRA test) simple randomization is applied to the sequence of the respective settings. This simple randomization is done automatically by the tool, the individual simple randomization can be examined afterwards.

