6.2.2 Blinding procedures

Trial participants will be blinded after assignment to interventions. The subjects will not know which hearing instrument technology they are wearing or which hearing instrument setting is activated during the respective testing (Please refer to section 6.1 General study design and justification of design). If possible double blinding will be executed with help of computer controlled testing procedures (e.g. software tool for MUSHRA Test).

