9.2.2 Assessment of secondary outcomes

ICH: Methods and timing for assessing, recording, and analysing of efficacy & safety parameters.

The secondary outcomes are the subjective test results of questionnaires during tests in real world environment (Reference to section 5.2 Secondary Outcomes). This includes home trials and may include guided walks. This assessment will be done between the appointments (home trials) and/or at specifically defined study appointments (guided walks). Depending on the investigated sound changing principle the suited outcome measurement is chosen. With the questionnaire as well the investigational application and the comparator are subjectively evaluated by the participants. Depending on the study part, the questionnaire will be filled out directly in the laboratory or in an home trial.

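### Section 12.1.1 lets an investigator who will usually know the hearing-aid setting correct a participant's paper answers without the participant's confirmation

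*Combined protocol and SAP*

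**What the plan says.** Section 12.1.1 (Case Report Forms) records study data on paper and electronic forms. For corrections on paper that it regards as self-evident, "either the subject does it by himself or the investigator undertakes the correction by crossing out the word/sentence". The strike-through is a single horizontal line, and the correction carries the corrector's identifier and the date. The same section provides that paper "data are entered into an electronic file for analysis by the respective investigator" and that an assigned monitor then checks them.

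On blinding, section 6.1 describes the design as "controlled, single blinded (participants), randomised (sequence of test procedure and sequence of tested setting/device") and adds: "The tests will be at least single blinded". Section 6.2.2 goes further only conditionally: "If possible double blinding will be executed with help of computer controlled testing procedures".

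On outcomes, section 9.2.2 makes real-world questionnaire results the secondary outcomes: "With the questionnaire as well the investigational application and the comparator are subjectively evaluated by the participants". The questionnaires are completed in the laboratory or at home. In Table 4 (section 5.1), rating scales, semantic differentials and interviews are among the primary methods for sub-studies of sound quality / hearing comfort.

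**The concern.** A rating, a yes/no reply or a comment is the participant's opinion. A date or an ID can be checked against something outside the form; an opinion cannot, so an error in it is seldom evident to anyone but its author. If a person who knows the active setting decides that an answer is a slip and replaces it, that person's expectation has a way into a self-reported outcome. The way in can favour one condition over the other, because the corrector may know which condition the answer belongs to. At stake is the novel-minus-comparator difference on outcomes for which the participant's blinding is the main protection.

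**Working it through.** The plan states no figure on this point and no calculation applies. The check is to read the sections against each other.

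**1. Whose entries are on the forms?** Section 12.1.1 names the participant as a possible corrector, which implies that participants write on these forms. It speaks of striking out a word or sentence, so it is not confined to clerical fields. Section 12.1.2 counts data recorded directly on the forms as source data. No section says outright that outcome questionnaires are paper case report forms. It is a reasonable inference, and the plan gives no other correction rule for participants' answers.

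**2. What does the corrector know?** Sections 6.1 and 6.2.2 require blinding of participants only. Section 9.3.2 places fitting and fine-tuning of the instruments in the study appointment, and section 9.3.3 applies the same procedure to the main study, so the staff present will usually know the setting. Section 6.2.1 adds: "Randomization and concealment of randomization list is generated by the Principle Investigator". Section 12.1.1 authorises every team member to make form entries, so the corrector need not be the fitter. Nothing requires the corrector to be blinded either.

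**3. What confirmation is required?** None. Section 12.1.1 does not ask the participant to see, initial or agree to an investigator's change. It does not say which answer is analysed, or whether corrections are counted and reported.

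**4. Would the later checks catch a biased change?** The investigator enters the data. The monitor belongs to the sponsor (section 1.5), and section 12.3 leaves the extent of source data verification to each sub-study. Verification compares the file with the form. Where the form carries a properly identified and dated correction, the two agree, and the check passes whether or not the participant meant the new answer.

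**5. Which outcomes are reached?**

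| Outcome | How captured | Reached by the paper rule? |
|---|---|---|
| Laboratory tests run by a measurement tool | Stored automatically (sections 9.2.1, 12.1) | No |
| Computer-run ratings, e.g. MUSHRA | By the software tool (sections 6.1, 6.2.1) | No |
| Real-world questionnaires (secondary) | Completed in the laboratory or at home (section 9.2.2); medium not stated | Yes, if on paper |
| Sound quality / hearing comfort ratings and interviews, where primary | Medium not stated for each method (Table 4) | Only if on paper |

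**The case against.** The rule is narrower and better guarded than a quick reading suggests. It covers self-evident corrections only. The single line is meant to leave the original entry readable, and each change is attributed and dated. Paper data are monitored, and section 6.2.3 has investigators sensitised to bias. A reader could fairly call this ordinary form-correction practice. Much of that stands: the change is traceable and could be reversed. It does not show that the replacement answer is the participant's.

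Four stronger readings are tempting, and the documents do not support them.

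- *Investigators may rewrite answers at will.* The permission is limited to self-evident corrections. Changing a rating because it conflicts with a comment would need interpretation and is not plainly allowed. The weakness is that the limit is undefined.
- *The corrector always knows the setting.* Single blinding is a minimum, double blinding is used where possible, and any team member may make entries. The supportable word is usually.
- *Primary results in general are exposed.* Automatically stored results lie outside the rule; only a primary rating or interview taken on paper is within it.
- *The false-positive rate rises by a known amount.* That needs an assumed shift. For instance, a spurious mean shift of 0.2 SD of the paired difference would raise the rejection rate of a two-sided 5% paired t-test to 13.6% (n = 20) or 16.1% (n = 25). But 0.2 × 20 = 4 and 0.2 × 25 = 5, so corrections would have to total a net 4 to 5 SDs in one direction. Nothing in the documents suggests this. Section 11.2 also says the secondary objective is handled mainly descriptively, so for most exposed outcomes the consequence would be a shifted reported difference, not a rejection rate.

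**Conclusion.** The point holds as a minor data-integrity gap. Section 12.1.1 states a rule under which a participant's paper answer can be replaced, without the participant's confirmation, by someone who is not required to be blinded and will usually know the condition. This rests on two inferences: that outcome questionnaires or ratings are at least sometimes paper case report forms, and that the team member making the correction usually knows the setting. Both are reasonable; neither is stated. The direction and size of any bias cannot be derived from the documents, and there is no evidence that it would be large. The case for acting is that the gap is avoidable at almost no cost, since the participant is available to confirm what was meant.

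**What to change.** Add to section 12.1.1:

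- Participant-reported outcome answers (ratings, scale points, yes/no replies, comments) may be changed only by the participant, or with the participant's dated confirmation.
- If a query about such an answer is not resolved, the original answer is the one analysed.
- Investigators may still correct administrative fields, such as a date or an ID, and fields they recorded themselves, under the existing strike-through rule.

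This needs no extra staff and no change to design or sample size. The cost is a few queries to participants, and a few unclear answers that stay as written.

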12.1.2 Specification of source documents

(ICH/E6 6.4.9)

ICH: The identification of any data to be recorded directly on the CRFs (i.e., no prior written or electronic record of data), and to be considered to be source data.

Source data are available at the site to document the existence of the study participants and can be found as described in section 12.1. The source data include the original documents relating to the study as follows:

- Demographic data / audiological history
- Visit dates
- Informed Consent Forms
- Randomisation number
- AEs/SAEs
- Device Deficiencies (DD)
- Results of relevant measurements
- Directly recorded data in p/eCRFs

12.1.3 Record keeping / archiving

(ICH/E6 6.13)

ICH: Data Handling and Record Keeping

All study data will be archived for a minimum of 10 years after study termination or premature termination of the clinical trial. The location of storage is on SharePoint as well in the archive at Sonova AG, Stäfa, as explained in section 12.1.

12.2 Data management

(ICH/E2; AGEK 12.2; SPIRIT #19)

This section describes plans for data entry, coding, security, and storage, including any related processes to promote data quality.

12.2.1 Data Management System

The data management is carried out as described in section 12.1 with help of a data management system. Data management systems that may be applied are the database IBM Clinical Development (former eClinicalOS), the SharePoint Web Application (Microsoft) and the SQL server (Microsoft). The EDC system gets verified and validated by the study team in the form of User Acceptance Tests (UAT) prior to each study start to ensure a proper working of the solution for the user. In addition, the study team accesses a permanent SharePoint site which is verified as well as validated and the filing of the documents follows a predefined scheme. The SQL server working in the background is controlled by the IT at Sonova AG, Stäfa.

12.2.2 Data security, access and back-up

Data security is fully granted, the access is limited to specified persons and both systems IBM Clinical Development and SharePoint undergo a daily backup on appropriate servers.

12.2.3 Analysis and archiving

Data are extracted via the Microsoft SQL server and can be converted to an arbitrary format, e.g. xls file. For the data analysis, different programs are used such as Microsoft Excel, SPSS, Statistica and MatLab. Archiving is done according to section 12.1 for a minimum of 10 years.

12.2.4 Electronic and central data validation

The data is validated by the monitor.

12.3 Monitoring

(AGEK 12.1; SPIRIT #23)

During this Study the Monitor will perform the Monitoring on a regular base - including the initiation visit, the routine visit and the close-out visit - in order to ensure that the study is conducted in accordance to the clinical investigation plan, further written procedures (if applicable), the ISO 14155:2011 as well as further applicable requirement. The extent and nature of the monitoring appropriate for the particular sub-study is assessed separately, including the strategy for source data verification. This will be based on considerations such as the objective, design, complexity, size critical data points and endpoints of the particular sub-study.

12.4 Audits and Inspections

(ClinO, Art. 58, 59; AGEK 12.1; SPIRIT #23)

The study documentation and the source data/documents are accessible to auditors/inspectors and questions are answered during inspections. All involved parties have to keep the participants data strictly confidential.

12.5 Confidentiality, Data Protection

(Clin O, Art. 18, 58; SPIRIT #27, 29)

Direct access to source documents will be permitted for purposes of monitoring (12.3), audits and inspections (12.4) (ICHE6, 6.10). Confidentiality and data protection is granted since access to the original data is only allowed to the study team, the monitor and the auditor. In case of publications by Sonova AG, the data is anonymized and no conclusion can be made to the subjects.

12.6 Storage of biological material and related health data

(Clin O, Art. 18; HVF Art. 28-32; SPIRIT #33)

N/A

13. PUBLICATION AND DISSEMINATION POLICY

(ICH/E6 6.15)

ICH: Publication policy, if not addressed in a separate agreement.

The results are documented in a final report and will be communicated to relevant employees of the Sonova AG. Occasionally parts of the results could be published in internal papers, specialised press (industry magazine), or in respective journals.

14. FUNDING AND SUPPORT

(Clin O, Art. 25i; ICH/E6 6.14; SPIRIT #4)

This section provides a brief statement of sources and types of financial, material, and other support for the trial.

14.1 Funding

(Clin O, Art. 25i)

ICH: Financing and insurance if not addressed in a separate agreement.

All sources and types of financial support for the study is provided by the Sponsor, Sonova AG.

14.2 Other Support

(Clin O, Art. 25i)

ICH: Financing and insurance if not addressed in a separate agreement.

All material is provided by the Sponsor, Sonova AG.

15. INSURANCE

(Clin O Art 12, 13; ICH/E6 6.14, AGEK 10.3; SPIRIT #30)

ICH:and insurance if not addressed in a separate agreement.

Category A studies are exempt hence no insurance is required. However, insurance will be provided by the Sponsor, Sonova AG: Police (Nr. CHCANA00770) „Versicherung für klinische Versuche in der Humanforschung“ from the insurance broker KESSLER & CO AG [name]. A copy of the specific certificate for each study part is filed in the ISF.

17. APPENDICES

ICH: (NOTE: Since the protocol and the clinical trial/study report are closely related, further relevant information can be found in the ICH Guideline for Structure and Content of Clinical Study Reports.)

N/A
